3.6 Intervention: AI-Assisted Algorithm-Supported Adaptive Simulation

Participants assigned to the intervention group received physiology instruction through a **screen-based adaptive simulation learning environment** incorporating AI-assisted educational feedback over a **12-week period**. The simulation-based instruction replaced conventional lecture-based teaching for selected physiology topics during the intervention phase.

Intervention Dosage:

- **Total instructional exposure:** 24 hours across 12 weeks

- **Session format:** 2 hours/week × 12 weeks
- **Case exposure:** Approximately 48-72 simulation cases spanning 8 physiological systems

Simulation Session Structure

Each session comprised three phases:

Phase 1: Pre-Briefing (15 minutes)

Facilitator-led orientation including: introduction to simulation interface, clarification of session objectives, establishment of psychological safety, review of learner expectations, and confirmation of technical readiness.

Phase 2: Individual Simulation Activity (90 minutes)

Participants independently completed multiple physiology-focused clinical case scenarios. Each case followed a structured instructional workflow:

1. **Clinical Scenario Presentation** — Patient scenario with clinical history, simulated vital signs, laboratory findings, and animated visualizations of physiological processes.
2. **Hypothesis Generation** — Participants identified potential physiological explanations for presented clinical findings.
3. **Diagnostic Decision** — Learners selected appropriate diagnostic investigations and interpreted simulated physiological data.
4. **Therapeutic Decision-Making** — Participants selected management strategies and predicted physiological consequences.
5. **Adaptive Feedback** — Automated formative feedback explaining reasoning errors, clarifying physiological mechanisms, and highlighting key learning concepts.
6. **Case Progression** — Subsequent cases adaptively adjusted in complexity according to learner performance.

Approximately **4-6 cases were completed per session.**

Phase 3: Facilitated Debriefing (15 minutes)

Faculty-led small-group debriefing sessions (8-10 learners) using a structured reflective framework encompassing **reaction, description, analysis, and application phases**. An advocacy-inquiry approach was employed to explore learner reasoning, correct misconceptions, and promote transfer of learning.

AI-Assisted Algorithm-Supported Adaptation Logic

The "AI-assisted" component refers to **predefined rule-based adaptive instructional functions** designed to personalize learning according to participant performance. The system automatically adjusted case difficulty, selected feedback pathways, and sequenced

subsequent learning tasks based on learner responses using faculty-defined instructional rules.

Adaptive Thresholds:

Performance Accuracy	System Response
> 80%	Progress to advanced case with increased complexity, competing pathophysiological mechanisms, and multi-step reasoning challenges
60-80%	Maintain moderate complexity; standard progression
< 60%	Trigger scaffolding: simplified case variants, targeted conceptual prompts, expanded explanatory feedback

The adaptive system maintained learner success rates within an approximate **60-80% performance window** to balance cognitive challenge and learner confidence per cognitive load theory and self-efficacy principles.

Important clarification: The platform did NOT use autonomous content generation, machine learning prediction models, natural language processing, or independent clinical decision-making functions.

Physiological Systems Covered (8 Core Systems)

1. Cardiovascular System
2. Respiratory System
3. Renal System
4. Neurological System
5. Endocrine System
6. Gastrointestinal System
7. Musculoskeletal System
8. Integumentary System

Simulation Fidelity

- **Conceptual fidelity:** All scenarios developed and reviewed by physiology faculty for scientific accuracy and curricular alignment.

- **Psychological fidelity:** Realistic patient narratives, simulated vital signs, laboratory findings, and time-pressured decision points.
- **Environmental fidelity:** High-quality digital visualizations and dynamic graphical representations of physiological processes.

3.7 Control Group: Conventional Teaching

Participants assigned to the control group received **standard curriculum-based physiology instruction** over the same 12-week study period, covering equivalent physiological systems with comparable instructional exposure (~24 hours). Instruction comprised:

- Didactic lectures covering foundational physiological mechanisms, system integration, and applied physiological interpretation
- Prescribed textbook readings assigned weekly
- Faculty-guided tutorial sessions involving structured clarification of physiological concepts and small-group discussion
- Scheduled laboratory practicals involving supervised physiological measurements and observation

The control condition did **not** include adaptive case sequencing, algorithm-supported instructional adaptation, automated formative feedback, interactive simulation-based clinical reasoning tasks, animated physiological visualization environments, or structured simulation debriefing. Participants in the control group did not have access to the adaptive simulation platform during the study period.

Following study completion, optional access to selected simulation learning resources was offered to the control group to address ethical considerations related to educational equity.

3.8 Assessment & Outcome Measures

All outcomes were assessed at three predefined time points:

- **Baseline (Week 1, Time 1)** — prior to intervention
- **Post-Intervention (Week 13, Time 2)**
- **Follow-up (Week 17, Time 3)** — four weeks post-intervention

Assessments were administered **online** using a secure institution-approved platform under standardized testing conditions.

3.8.1 Primary Outcomes

1. Physiological Knowledge (Physiological Knowledge Test - PKT)

- 40-item multiple-choice assessment covering 8 core physiological systems
- Designed to evaluate higher-order conceptual application and physiological interpretation
- Cronbach's $\alpha = 0.89$ (good internal consistency)
- Time Frame: Baseline, Post-Intervention, 4-week Follow-up

2. Physiological Reasoning Ability (Physiological Reasoning Ability Test - PRAT)

- Scenario-based assessment comprising clinical vignettes
- Tasks: hypothesis generation, interpretation of physiological data, application to management decisions
- Scored using a four-point analytic rubric (hypothesis generation, physiological explanation, diagnostic interpretation, management justification)
- Inter-rater reliability: ICC = 0.91 (excellent)
- Two blinded raters independently scored responses
- Time Frame: Baseline, Post-Intervention, 4-week Follow-up

3.8.2 Secondary Outcomes

3. Conceptual Understanding (Physiological Concepts Inventory - PCI)

- Faculty-developed physiology concept inventory distinguishing deep conceptual understanding from surface-level memorization
- Covers all 8 physiological systems
- Cronbach's $\alpha = 0.84$ (good internal consistency)
- Higher scores indicate deeper conceptual understanding
- Time Frame: Baseline, Post-Intervention, 4-week Follow-up

4. Student Engagement (University Student Engagement Inventory - USEI)

- Assesses behavioral, emotional, and cognitive dimensions of learner engagement
- Higher scores indicate greater engagement
- Cronbach's $\alpha = 0.88$
- Time Frame: Baseline, Post-Intervention, 4-week Follow-up

5. Cognitive Load (NASA Task Load Index - NASA-TLX)

- Multidimensional measure of perceived cognitive workload
- Higher scores reflect greater perceived workload and task demand
- Cronbach's $\alpha = 0.82$
- Time Frame: Baseline, Post-Intervention, 4-week Follow-up

6. Academic Self-Efficacy (College Academic Self-Efficacy Scale - CASES)

- Adapted version assessing learner confidence in physiology-related academic tasks and simulation-based learning activities
- Higher scores indicate greater academic self-efficacy
- Cronbach's $\alpha = 0.86$
- Time Frame: Baseline, Post-Intervention, 4-week Follow-up

4. Statistical Analysis Plan (SAP)

All statistical analyses were performed using **IBM SPSS Statistics version 22.0** (IBM Corp., Armonk, NY, USA). All tests were two-tailed, with statistical significance set at $\alpha = 0.05$.

Effect size conventions:

- Cohen's d / f : 0.20 (small), 0.50 (medium), 0.80 (large)
- Partial eta squared (η^2p): 0.01 (small), 0.06 (medium), 0.14 (large)

All randomized participants were included in final analyses according to the **intention-to-treat (ITT) principle**.

4.1 Primary Outcomes

Descriptive statistics:

- Normally distributed continuous data: mean and standard deviation (SD)
- Non-normally distributed data: median and interquartile range (IQR)
- Categorical data: frequencies and percentages

Assumption testing:

- Normality: Shapiro-Wilk test and visual inspection of Q-Q plots
- Homogeneity of variances: Levene's test
- Sphericity: Mauchly's test; Greenhouse-Geisser correction applied when violated ($p < 0.05$)
- Baseline equivalence: independent-samples t-tests (continuous) and chi-square tests (categorical)
- Missing data patterns: Little's MCAR test

Primary inferential analysis:

- **Repeated-measures ANOVA** to examine main effects of time, group, and time \times group interaction for:
 - Physiological Knowledge Test (PKT)
 - Physiological Reasoning Ability Test (PRAT)
- Significance threshold: $p < 0.05$
- Post-hoc: **Bonferroni-adjusted pairwise comparisons** when significant effects identified
- Effect sizes: partial eta squared (η^2p) for omnibus tests; Cohen's d for pairwise comparisons

Additional analysis:

- **Multiple linear regression** to explore predictors of follow-up physiological knowledge (PKT) scores, controlling for: baseline PKT, prior digital experience, prior AI tool exposure, post-intervention engagement (USEI), and post-intervention cognitive load (NASA-TLX)
- Multicollinearity assessed using tolerance values and variance inflation factors (VIF)

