3.3 Sample Size Determination

Sample size estimation was performed using **G*Power version 3.1.9.7** for repeated-measures analysis of variance (ANOVA) with a within-between interaction.

Parameters assumed:

- Effect size: medium ($f = 0.25$)
- Type I error rate (α): 0.05
- Statistical power: 0.95
- Number of groups: 2
- Measurement occasions: 3
- Correlation among repeated measures: 0.5

Calculated minimum sample: 292 participants per group.

Final target enrollment: 336 participants per group (accounting for an anticipated 15% attrition rate), yielding a **total sample size of 672 participants**.

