3.5 Randomization and Blinding

Randomization: Following completion of baseline assessments, participants were randomly allocated in a 1:1 ratio using a **computer-generated random sequence**, stratified by academic program to ensure balanced group representation.

Allocation Concealment: Maintained through **sequentially numbered, opaque, sealed envelopes** prepared by an independent researcher not involved in recruitment or assessment.

Blinding: Outcome assessors and data analysts were blinded to group allocation throughout the study. Blinding was maintained during the scoring and data analysis processes.

Contamination Control: Participants were instructed not to share intervention materials, simulation access, or case content with peers assigned to the alternate study condition during the study period.

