4.3 Missing Data

Six participants (three per group) were lost prior to the Time 3 follow-up assessment. Missing follow-up values for participants lost prior to the Time 3 assessment were handled using the **Last Observation Carried Forward (LOCF)** method in accordance with the intention-to-treat principle. Specifically, the most recent available participant outcome values were carried forward for follow-up analyses to preserve randomized group allocation and maintain complete repeated-measures datasets for statistical analysis.

Participants who withdrew from intervention participation permitted retention and analysis of previously collected de-identified study data in accordance with the approved consent process and institutional ethics approval.

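### The primary repeated-measures ANOVA leaves baseline unadjusted and omits academic program, so it gives up precision that the collected data could supply at no cost

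*Combined protocol and SAP*

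**What the plan says.** - **Model.** Section 4.1 sets a repeated-measures ANOVA for PKT and PRAT "to examine main effects of time, group, and time" by group interaction. It names no covariate and no stratum. Section 4.2 uses the same method for the secondary scales.
- **Baseline as a level.** Section 3.8.1 gives each primary outcome as "Time Frame: Baseline, Post-Intervention, 4-week Follow-up", and section 3.3 sizes the trial with "Measurement occasions: 3". Section 3.5 places randomisation after the baseline assessments.
- **Stratum.** Section 3.5 says that allocation was "stratified by academic program to ensure balanced group representation". Section 3.2 lists four programs. Program appears in no analysis.
- **Missing Week 17 values.** Section 4.3 reports six losses, three per group, and says that "the most recent available participant outcome values were carried forward for follow-up analyses".
- **Other uses of baseline.** Section 4.1 plans significance tests of baseline equivalence. It adjusts for baseline PKT only in an additional regression of follow-up PKT, whose listed predictors include neither group nor program.
- **Reported effects.** These are partial eta squared and Cohen's d. No adjusted arm difference with a confidence interval is requested.

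**The concern.** The trial asks how far the arms differ after teaching. Three features of the plan answer that less well than the data allow.

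1. No treatment effect is possible at baseline. The group main effect averages that visit in. The interaction uses baseline only by subtraction, which is less efficient than regression adjustment unless the correlation is close to 1. Arm comparisons at Week 13 or 17, if those are among the post-hoc comparisons, would not use baseline at all.
2. Stratified allocation balances program between arms. If the model then omits program, between-program variance stays in the error term of between-arm tests.
3. Repeated-measures ANOVA needs complete records, which is why values are carried forward. At a retention visit, that assumes no change since the last assessment and treats filled values as observed.

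At stake are the width of the intervals and the clarity of the estimate. Testing baseline differences after randomisation does not replace adjustment.

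**Working it through.** **Inputs.** From section 3.3: correlation ρ = 0.5, α = 0.05, f = 0.25, three occasions and a target of 336 per arm (672 in total). From section 4.3: six losses, three per arm. Assumed here: all 672 were randomised, compound symmetry with SD 1, a constant effect d at Weeks 13 and 17, and four equal strata. The documents give no program R², so a range is shown.

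**The plan's own figure.** The plan states no precision for its analysis. Its sample size does not reproduce: with λ = f²·N·3/(1−ρ) and df 2 and 2(N−2), N = 44 in total gives λ = 0.0625 × 44 × 3/0.5 = 16.5 and power of 95.6%, against the stated 292 per group. That is a separate matter. The comparisons below use only ρ and 336 per arm.

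**Information, in units of (N/4)d².**

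| Analysis | Effect | Variance | Information |
|---|---|---|---|
| Group main effect (three visits) | 2d/3 | (1+2ρ)/3 = 0.667 | 0.444/0.667 = 0.67 |
| Mean of Weeks 13 and 17 minus baseline | d | 0.75 + 1 − 2(0.5) = 0.75 | 1.33 |
| Mean of Weeks 13 and 17, baseline-adjusted | d | 0.75 − 0.5² = 0.50 | 2.00 |

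The ratio of the adjusted analysis to the change contrast is 1.5 at ρ = 0.5. It is 1.25 at 0.7 and 1.15 at 0.8.

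**One visit.** The variance is 1 unadjusted, 2(1−ρ) = 1 for change, and 1−ρ² = 0.75 adjusted. With √(2/336) = 0.0772, the SE falls from 0.077 to 0.067 SD: 25% less variance and a 13% smaller SE. Against change, the SE ratio is √((1+ρ)/2), a cut of 19%, 13%, 8% and 5% at ρ = 0.3, 0.5, 0.7 and 0.8. Adding program at R² = 10%, the adjusted variance is 0.9 − 0.4²/0.9 = 0.722 and the SE is 0.066 SD, so nearly all the gain comes from baseline.

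**Power, N/4 = 168.**

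- d = 0.20: 168 × 0.04 = 6.72. Multiplying by 0.67, 1.33 and 2.0 gives noncentralities of 4.48, 8.96 and 13.44, and 1-df power of 56%, 85% and 96%. The 2-df interaction test, also with noncentrality 8.96, has 77%. One visit gives 74% unadjusted or by change, and 85% adjusted for baseline.
- d = 0.50 (one reading of f = 0.25): 168 × 0.25 = 42. Even the group main effect has noncentrality 28 and power above 99.9%.

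**Omitting program.** In a single-visit arm comparison, the reported SE is too large by 1/√(1−R²), so true size is P(|Z| > 1.96/√(1−R²)):

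| Assumed R² | SE too large by | True size of a 5% test |
|---|---|---|
| 10% | 5% | 3.9% |
| 20% | 12% | 2.8% |
| 30% | 20% | 1.9% |

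A simulation of 4,000 trials agreed: 3.7% at R² = 10% and 1.8% at 30%, with simulation error of about 0.3 to 0.4 points. In the same trials the time by group test rejected a true null 5.3 to 5.5% of the time, and the change contrast had a model SE of 0.0771 against an empirical 0.0781. A program effect that is constant over time cancels within student.

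**LOCF.** 3/336 = 0.9% per arm. If one arm truly declines by 0.20 SD between Weeks 13 and 17, the bias is 0.0089 × 0.20 = 0.002 SD, against an SE of 0.066.

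**The case against.** The strongest reply is that the trial was sized on the time by group interaction, and that test is valid. This stands. The group main effect is listed in section 4.1 but is not the test the sample size addresses, so the fair comparison is 2.0 against 1.33, not against 0.67.

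A reader might infer that the plan's standard errors are wrong or that false positives are inflated. The documents do not support that. Omitting program leaves the interaction test unharmed if program effects are constant over time, and elsewhere the error is conservative. Its size depends on an R² that the documents do not give.

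Section 4.1 also does not say whether its pairwise comparisons are between arms at each visit or within arms over time. The figures for unadjusted arm comparisons therefore apply only if such comparisons are made.

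On LOCF, a reader might infer that carrying values forward distorts the retention result. With 0.9% missing and three losses in each arm, it cannot do so to any visible degree. Nor does section 4.3 say that the carried value is always from Week 13; it could be baseline for a student lost earlier.

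Finally, modelling baseline as an outcome is not in itself the fault, since a mixed model with a common baseline mean does so too. The gain comes from the equal-baseline constraint or the covariate. None of this removes the loss of precision.

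**Conclusion.** The point holds as a loss of precision. It should be fixed, but it is not a fault of validity. At ρ = 0.5, baseline adjustment gives 1.5 times the information of the interaction contrast on the mean of Weeks 13 and 17, and a 13% smaller SE at one visit (5 to 19% smaller than for change over assumed ρ from 0.8 to 0.3). The group main effect shrinks a constant effect to two thirds. Program belongs in the model because allocation was stratified on it, though it adds little once baseline is in, unless its R² is large. LOCF is a minor point of principle.

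These figures rest on compound symmetry, a constant effect after teaching, 672 randomised and assumed program R² values. A reader might infer that the trial's conclusion would change. At the planned f = 0.25, read as d = 0.5, power is already near 100% under every analysis considered. The gain would matter for much smaller effects and for the width of the intervals.

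**What to change.** Add a linear mixed model for PKT and PRAT, and for the secondary scales, on all observed data. Include:

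- baseline as a covariate, or a baseline mean common to both arms
- program as a fixed effect
- arm-by-visit terms at Weeks 13 and 17
- an unstructured within-student covariance
- no LOCF.

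Report the adjusted arm difference with its 95% confidence interval at each of the two visits.

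The status of this model depends on timing. The opening of section 4 and section 4.3 describe the analysis as done, although section 4.2 uses the future tense. Make the mixed model primary only if it was fixed before unblinding. Otherwise keep the stated repeated-measures ANOVA as primary and report the new model beside it as a labelled sensitivity analysis. The baseline significance tests can be dropped in favour of descriptive summaries; that is a reporting preference.

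The cost is SAP wording and analysis syntax; no new data are needed. The change does not settle which visit or contrast is primary, or how two primary outcomes each tested at 0.05 are handled. The SAP should state both separately.

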2.1 Background & Aims

Healthcare professionals are required to integrate foundational physiological knowledge with clinical reasoning to ensure safe and effective patient care. A persistent challenge in health sciences education is the gap between students' ability to recall physiological concepts and their capacity to apply this knowledge meaningfully in clinical decision-making contexts. This theory-practice disconnect has been consistently reported across nursing and allied health education and is associated with reduced clinical preparedness and learner confidence.

Traditional preclinical physiology education commonly relies on curriculum-based instructional approaches centered on didactic teaching, textbook-directed learning, tutorials, and laboratory practical activities. Although such approaches may facilitate short-term knowledge acquisition, they are often insufficient for promoting higher-order cognitive processes, including interpretation, integration, and application of physiological principles in clinical contexts. Consequently, students may demonstrate adequate theoretical understanding yet experience difficulty explaining physiological mechanisms underlying patient presentations or justifying clinical decisions.

Aims of this study:

- To evaluate the effectiveness of AI-assisted algorithm-supported adaptive screen-based simulation compared with conventional physiology instruction on physiological knowledge acquisition and reasoning ability among undergraduate health science students.
- To assess the impact of the intervention on secondary outcomes including conceptual understanding, learning engagement, cognitive load, and academic self-efficacy at post-intervention and four-week follow-up.

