4.2 Secondary Outcomes

Repeated-measures ANOVA will be conducted for each secondary outcome:

- Physiological Concepts Inventory (PCI)
- University Student Engagement Inventory (USEI) — overall and subscales (Behavioral, Cognitive, Emotional)
- NASA Task Load Index (NASA-TLX)
- Academic Self-Efficacy (ASE/CASES)

Statistical significance threshold: $p < 0.05$. Bonferroni-adjusted post-hoc analyses will follow significant effects. Effect sizes reported using partial eta squared (η^2p).

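### The exploratory regression of follow-up PKT names no term for randomised arm, so post-intervention engagement and workload can appear as predictors only because the arms differ

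*Combined protocol and SAP*

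**What the plan says.** Under the additional analysis in section 4.1, the plan sets out one regression, "to explore predictors of follow-up physiological knowledge (PKT) scores, controlling for: baseline PKT, prior digital experience, prior AI tool exposure, post-intervention engagement (USEI"). The list then ends "and post-intervention cognitive load (NASA-TLX"). That makes five covariates, and arm is not among them. No arm interaction and no separate fit by arm is mentioned. The one model check given is "Multicollinearity assessed using tolerance values and variance inflation factors (VIF").

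The same section does name arm for the repeated-measures ANOVA, which is "to examine main effects of time, group, and time" by group.

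The opening of section 4 says "All randomized participants were included in final analyses according to the" intention-to-treat principle, and "All tests were two-tailed, with statistical significance set at" 0.05.

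One aim in section 2.1 is "To assess the impact of the intervention on secondary outcomes including conceptual understanding, learning engagement, cognitive load, and academic self-efficacy". Section 3.8.2 lists USEI and NASA-TLX as secondary outcomes, and under section 4.2 "Repeated-measures ANOVA will be conducted for each secondary outcome".

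**The concern.** Two of the five covariates are measured at Week 13, after 12 weeks of randomised instruction, and the trial's own aims say the intervention may change them. If it shifts both engagement and knowledge, arm is a common cause of the covariate and the outcome. A model across both arms without an arm term then gives USEI (or NASA-TLX) a coefficient that mixes two things: the association among students taught the same way, and the difference between arms.

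At stake is a reported finding that engagement or perceived workload predicts knowledge at Week 17 when no such relation exists within either arm. Tolerance and VIF would give no warning, because they describe correlation among the covariates in the model and cannot reveal one that was left out.

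**Working it through.** The documents state no figure for this regression, so there is none to reproduce. The check asks how often the listed model would flag USEI or NASA-TLX when neither has any within-arm relation to follow-up PKT.

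**Inputs from the documents**
- 336 per arm, N = 672 (section 3.3).
- Correlation among repeated measures 0.5 (section 3.3), used here as the baseline to follow-up PKT correlation.
- Two-sided 0.05 (opening of section 4).

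**Assumed, because the documents give no value**
- Arm differences in within-arm SD units: dY on follow-up PKT, dU on USEI, dT on NASA-TLX. A range is shown. The SAP's own convention calls a Cohen's d of 0.20 small, 0.50 medium and 0.80 large.
- Within-arm slopes of PKT on USEI and on NASA-TLX: zero.

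**Formula, USEI alone shifted by arm**

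With 1:1 allocation, arm contributes 0.25·dY·dU to the covariance of PKT and USEI, and 0.25·dU² to the variance of USEI. Without an arm term:
- spurious slope b = 0.25·dY·dU / (1 + 0.25·dU²)
- residual variance v = (1 − 0.5²) + 0.25·dY² − b·0.25·dY·dU
- standard error = √[v / (672·(1 + 0.25·dU²))]
- false-positive rate = P(|Z + b/SE| > 1.96)

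At 0.5 SD on both:
- b = 0.0625/1.0625 = 0.059
- v = 0.75 + 0.0625 − 0.0037 = 0.809
- SE = √(0.809/714) = 0.0337
- b/SE = 1.75, giving a rate of 41.6%

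| Difference on both PKT and USEI | b | b/SE | Rate by formula | Rate by numerical simulation |
|---|---|---|---|---|
| 0.2 SD | 0.010 | 0.30 | 6.0% | 5-6% |
| 0.3 SD | 0.022 | 0.66 | 10.1% | 10% |
| 0.5 SD | 0.059 | 1.75 | 41.6% | 40-42% |
| 0.8 SD | 0.138 | 4.09 | 98.3% | 98% |

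**NASA-TLX also shifted by arm**

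With equal and opposite shifts of size d on USEI and NASA-TLX, and d on PKT, b = 0.25·d² / (1 + 0.5·d²):
- d = 0.5: 0.0625/1.125 = 0.056
- d = 0.8: 0.16/1.32 = 0.121

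Numerical simulation (2,000 trials, all five listed covariates) gave mean slopes of +0.056 and −0.055 at 0.5 SD, and +0.122 and −0.121 at 0.8 SD, in agreement with the formula. The false-positive rates were:

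| Difference on all three | USEI / NASA-TLX, no arm term | USEI / NASA-TLX, arm added |
|---|---|---|
| 0.2 SD | 5.5% / 6.2% | 4.2% / 4.8% |
| 0.5 SD | 37.6% / 37.6% | 5.4% / 3.9% |
| 0.8 SD | 95.0% / 94.9% | 5.3% / 4.4% |

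With arm in the model, the mean slopes return to about 0.00.

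**Where the problem disappears**

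If dY or dU is zero, b is zero. In simulation without an arm term, the rates were:
- 0.5 SD on PKT only: 4.8% (USEI) and 4.2% (NASA-TLX)
- 0.5 SD on USEI and NASA-TLX only: 4.5% for each

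Unequal differences fall in between:
- 0.5 SD on PKT and 0.2 SD on USEI: 11.5%
- 0.8 SD on PKT and 0.2 SD on USEI: 18.6%

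**The case against.** **The plan does not say that arm was left out.** The list is worded as control variables and no predictor of interest is named, so arm could be the unstated predictor. This stands. A reader might infer that the plan states a pooled model without arm, but that is inference: from a single regression, from the intention-to-treat statement, and from group being named only for the ANOVA. The other reading has its own fault. An arm coefficient adjusted for Week 13 USEI and NASA-TLX conditions on variables the intervention may have changed, so it would not be the randomised effect. Both readings call for the model to be stated.

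**A pooled coefficient is a legitimate description.** Across all students, engagement may predict knowledge at follow-up whatever the reason, and the plan claims no within-arm or causal relation. This stands in part: the 5% benchmark belongs to a within-arm null that the plan does not state. But the text offers nothing to stop a reader taking a significant engagement coefficient as a relation among similarly taught students, and exploratory labelling does not separate the two meanings.

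**The large rates need large assumptions.** This stands. A reader might take 98% as the expected error rate. The documents give no arm effects to support that, and the inflation is negligible at 0.2 SD or when only one variable differs.

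**Further demands might seem to follow**, such as adding academic program or dropping the carried-forward Week 17 scores. Nothing here shows that omitting program biases the USEI or NASA-TLX coefficients. Section 4.3 reports six losses, three per group; against 672 that is 6/672 = 0.9%. Neither demand is part of this point.

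**Conclusion.** The point holds in limited form. The regression names no term for randomised arm while including two post-intervention scores that the trial treats as outcomes. Fitted as listed to all randomised participants, it can report an arm difference as a predictor.

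The size depends on assumed arm differences, with no within-arm association and 336 per arm. For USEI it runs from about 5-6% (0.2 SD on both PKT and USEI) through 10% (0.3 SD) and 40% (0.5 SD) to 98% (0.8 SD). With NASA-TLX shifted as well, it is about 38% for each covariate at 0.5 SD and 95% at 0.8 SD. It requires arm differences on both PKT and the covariate.

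A reader might infer that the trial's treatment comparisons are compromised. They are not: the repeated-measures ANOVA of PKT and PRAT names group and its interaction with time, and the secondary outcomes have their own ANOVAs. The consequence is confined to one additional, exploratory analysis. The change is still worth making because it costs almost nothing.

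**What to change.** - State whether arm is in the model, and add it as a fixed term.
- Add an arm-by-USEI and an arm-by-NASA-TLX check. A single within-arm slope is meaningful only if the slopes are common; if they are not, report them by arm.
- Describe the USEI and NASA-TLX coefficients as exploratory within-arm associations. The arm term removes the artefact shown above but does not make these coefficients causal.
- State that the arm coefficient in this model is not the randomised treatment effect, because the model conditions on post-randomisation variables.

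The cost is one model term, two interaction checks and two sentences: three degrees of freedom out of 672 participants. No new data are needed, and the model can be re-run on the existing dataset.
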